14.3.1.2 Unsolicited Adverse Events

Table 118: Number and Percentage of Subjects Experiencing Unsolicited Adverse Events with 95% Confidence Intervals by MedDRA® System Organ Class and Preferred Term, and Treatment Group – Safety Population*

MedDRA® System Organ Class	MedDRA® Preferred Term	Group 1: Simultaneous Administration (N=X)		Group 2: Sequential Administration (N=X)		Group 3: HIV4 Only (N=X)	
		n	% (95% CI)	n	% (95% CI)	n	% (95% CI)
Any SOC	Any PT	x	xx (xx-xx)	x	xx (xx-xx)	x	xx (xx-xx)
[SOC 1]	Any PT						
	[PT 1]						
	[PT 2]						
[SOC 2]	Any PT						
	[PT 1]						
	[PT 2]						

Note: N = number of subjects in the Safety Analysis Population who received any dose. This table presents number and percentage of subjects. A subject is only counted once per PT.

Table 119: Number and Percentage of Subjects Experiencing Unsolicited Adverse Events by MedDRA® System Organ Class and Preferred Term, Maximum Severity, Relationship, and Treatment Group – Safety Population*

Treatment Group	MedDRA® System Organ Class	MedDRA® Preferred Term	Any Incidence		Severity [1]						Relationship to Treatment [2]			
					Mild		Moderate		Severe		Not Related		Related	
			n	%	n	%	n	%	n	%	n	%	n	%
Group 1: Simultaneous Administration (N=X)	Any SOC	Any PT	x	xx	x	xx	x	xx	x	xx	x	xx	x	xx
	[SOC 1]	Any PT												
		[PT 1]												
		[PT 2]												
	[SOC 2]	Any PT												
		[PT 1]												
		[PT 2]												
Group 2: Sequential Administration (N=X)	Any SOC	Any PT	x	xx	x	xx	x	xx	x	xx	x	xx	x	xx
	[SOC 1]	Any PT												
		[PT 1]												
		[PT 2]												
	[SOC 2]	Any PT												
		[PT 1]												
		[PT 2]												
Group 3: IIV4 Only (N=X)	Any SOC	Any PT	x	xx	x	xx	x	xx	x	xx	x	xx	x	xx
	[SOC 1]	Any PT												
		[PT 1]												
		[PT 2]												

Table 119: Number and Percentage of Subjects Experiencing Unsolicited Adverse Events by MedDRA® System Organ Class and Preferred Term, Maximum Severity, Relationship, and Treatment Group – Safety Population *(continued)*

Treatment Group	MedDRA® System Organ Class	MedDRA® Preferred Term	Any Incidence		Severity [1]						Relationship to Treatment [2]			
					Mild		Moderate		Severe		Not Related		Related	
			n	%	n	%	n	%	n	%	n	%	n	%
	[SOC 2]	Any PT												
		[PT 1]												
		[PT 2]												

Note: N = Number of subjects in the Safety Analysis Population.
 [1] For severity, a subject is counted once per preferred term and is summarized according to their highest severity.
 [2] For relationship, a subject is only counted once per preferred term and is summarized according to their closest relationship.

Table 120: Number and Percentage of Subjects Experiencing Non-Serious Related Unsolicited Adverse Events by MedDRA® System Organ Class and Preferred Term, Maximum Severity, and Treatment Group – Safety Population

Treatment Group	MedDRA® System Organ Class	MedDRA® Preferred Term	Any Incidence		Severity [1]					
			n	%	Mild		Moderate		Severe	
					n	%	n	%	n	%
Group 1: Simultaneous Administration (N=X)	Any SOC	Any PT	x	xx	x	xx	x	xx	x	xx
	[SOC 1]	Any PT	x	xx	x	xx	x	xx	x	xx
		[PT 1]								
		[PT 2]								
	[SOC 2]	Any PT								
		[PT 1]								
		[PT 2]								
Group 2: Sequential Administration (N=X)	Any SOC	Any PT	x	xx	x	xx	x	xx	x	xx
	[SOC 1]	Any PT	x	xx	x	xx	x	xx	x	xx
		[PT 1]								
		[PT 2]								
	[SOC 2]	Any PT								
		[PT 1]								
		[PT 2]								
Group 3: IIV4 Only (N=X)	Any SOC	Any PT	x	xx	x	xx	x	xx	x	xx
	[SOC 1]	Any PT	x	xx	x	xx	x	xx	x	xx
		[PT 1]								
		[PT 2]								
	[SOC 2]	Any PT								

Table 120: Number and Percentage of Subjects Experiencing Non-Serious Related Unsolicited Adverse Events by MedDRA® System Organ Class and Preferred Term, Maximum Severity, and Treatment Group – Safety Population *(continued)*

Treatment Group	MedDRA® System Organ Class	MedDRA® Preferred Term	Any Incidence		Severity [1]					
					Mild		Moderate		Severe	
			n	%	n	%	n	%	n	%
		[PT 1]								
		[PT 2]								

Note: N = Number of subjects in the Safety Analysis Population. This table presents number and percentage of subjects.
[1] For severity, a subject is counted once per preferred term and is summarized according to their highest severity.

Table 121: Number and Percentage of Subjects Experiencing Unsolicited Adverse Events Within 21 Days Post Dose by MedDRA® System Organ Class and Preferred Term, Day Post Dose, and Treatment Group – Safety Population

MedDRA® System Organ Class	MedDRA® Preferred Term	Day 1-8 Post Dose 1		Day 9-22 Post Dose 1		Day 1-22 Post Dose 1		Day 1-8 Post Dose 2		Day 9-22 Post Dose 2		Day 1-22 Post Dose 2		Day 1-8 Post Dose 3		Day 1-8 Post Dose 3		Day 1-8 Post Dose 3		Day 1-22 Post Any Dose	
		n	%	n	%	n	%	n	%	n	%	n	%	n	%	n	%	n	%	n	%
Group 1: Simultaneous Administration (N=X)																					
Any SOC	Any PT	x	xx	x	xx	x	xx	x	xx	x	xx	x	xx	NA	NA	NA	NA	NA	NA	x	xx
[SOC 1]	Any PT	x	xx	x	xx	x	xx	x	xx	x	xx	x	xx	NA	NA	NA	NA	NA	NA	x	xx
	[PT 1]	x	xx	x	xx	x	xx	x	xx	x	xx	x	xx	NA	NA	NA	NA	NA	NA	x	xx
	[PT 2]	x	xx	x	xx	x	xx	x	xx	x	xx	x	xx	NA	NA	NA	NA	NA	NA	x	xx
[SOC 2]	Any PT	x	xx	x	xx	x	xx	x	xx	x	xx	x	xx	NA	NA	NA	NA	NA	NA	x	xx
	[PT 1]	x	xx	x	xx	x	xx	x	xx	x	xx	x	xx	NA	NA	NA	NA	NA	NA	x	xx
	[PT 2]	x	xx	x	xx	x	xx	x	xx	x	xx	x	xx	NA	NA	NA	NA	NA	NA	x	xx
Group 2: Sequential Administration (N=X)																					
Any SOC	Any PT	x	xx	x	xx	x	xx	x	xx	x	xx	x	xx	x	xx	x	xx	x	xx	x	xx
[SOC 1]	Any PT	x	xx	x	xx	x	xx	x	xx	x	xx	x	xx	x	xx	x	xx	x	xx	x	xx
	[PT 1]	x	xx	x	xx	x	xx	x	xx	x	xx	x	xx	x	xx	x	xx	x	xx	x	xx
	[PT 2]	x	xx	x	xx	x	xx	x	xx	x	xx	x	xx	x	xx	x	xx	x	xx	x	xx
[SOC 2]	Any PT	x	xx	x	xx	x	xx	x	xx	x	xx	x	xx	x	xx	x	xx	x	xx	x	xx
	[PT 1]	x	xx	x	xx	x	xx	x	xx	x	xx	x	xx	x	xx	x	xx	x	xx	x	xx
	[PT 2]	x	xx	x	xx	x	xx	x	xx	x	xx	x	xx	x	xx	x	xx	x	xx	x	xx
Group 3: IIV4 Only (N=X)																					
Any SOC	Any PT	x	xx	x	xx	x	xx	NA	NA	NA	NA	NA	NA	NA	NA	NA	NA	NA	NA	x	xx
[SOC 1]	Any PT	x	xx	x	xx	x	xx	NA	NA	NA	NA	NA	NA	NA	NA	NA	NA	NA	NA	x	xx
	[PT 1]	x	xx	x	xx	x	xx	NA	NA	NA	NA	NA	NA	NA	NA	NA	NA	NA	NA	x	xx
	[PT 2]	x	xx	x	xx	x	xx	NA	NA	NA	NA	NA	NA	NA	NA	NA	NA	NA	NA	x	xx

Table 121: Number and Percentage of Subjects Experiencing Unsolicited Adverse Events Within 21 Days Post Dose by MedDRA® System Organ Class and Preferred Term, Day Post Dose, and Treatment Group – Safety Population (continued)

MedDRA® System Organ Class	MedDRA® Preferred Term	Day 1-8 Post Dose 1		Day 9-22 Post Dose 1		Day 1-22 Post Dose 1		Day 1-8 Post Dose 2		Day 9-22 Post Dose 2		Day 1-22 Post Dose 2		Day 1-8 Post Dose 3		Day 1-8 Post Dose 3		Day 1-8 Post Dose 3		Day 1-22 Post Any Dose		
		n	%	n	%	n	%	n	%	n	%	n	%	n	%	n	%	n	%	n	%	n
[SOC 2]	Any PT	x	xx	x	xx	x	xx	NA	NA	NA	NA	NA	NA	NA	NA	NA	NA	NA	NA	NA	x	xx
	[PT 1]	x	xx	x	xx	x	xx	NA	NA	NA	NA	NA	NA	NA	NA	NA	NA	NA	NA	NA	x	xx
	[PT 2]	x	xx	x	xx	x	xx	NA	NA	NA	NA	NA	NA	NA	NA	NA	NA	NA	NA	NA	x	xx

Note: N = Number of subjects in the Safety Analysis Population. This table presents number and percentage of subjects. For each time period, a subject is only counted once per PT.

Table 122: Number and Percentage of Subjects Experiencing Non-Serious, Related Unsolicited Adverse Events Within 21 Days Post Dose by MedDRA® System Organ Class and Preferred Term, Dose and Treatment Group – Safety Population

MedDRA® System Organ Class	MedDRA® Preferred Term	Day 1-8 Post Dose 1		Day 9-22 Post Dose 1		Day 1-22 Post Dose 1		Day 1-8 Post Dose 2		Day 9-22 Post Dose 2		Day 1-22 Post Dose 2		Day 1-8 Post Dose 3		Day 1-8 Post Dose 3		Day 1-8 Post Dose 3		Day 1-22 Post Any Dose	
		n	%	n	%	n	%	n	%	n	%	n	%	n	%	n	%	n	%	n	%
Group 1: Simultaneous Administration (N=X)																					
Any SOC	Any PT	x	xx	x	xx	x	xx	x	xx	x	xx	x	xx	NA	NA	NA	NA	NA	NA	x	xx
[SOC 1]	Any PT																				
	[PT 1]																				
	[PT 2]																				
[SOC 2]	Any PT																				
	[PT 1]																				
	[PT 2]																				
Group 2: Sequential Administration (N=X)																					
Any SOC	Any PT	x	xx	x	xx	x	xx	x	xx	x	xx	x	xx	x	xx	x	xx	x	xx	x	xx
[SOC 1]	Any PT																				
	[PT 1]																				
	[PT 2]																				
[SOC 2]	Any PT																				
	[PT 1]																				
	[PT 2]																				
Group 3: IIV4 Only (N=X)																					
Any SOC	Any PT	x	xx	x	xx	x	xx	NA	NA	NA	NA	NA	NA	NA	NA	NA	NA	NA	NA	x	xx
[SOC 1]	Any PT																				
	[PT 1]																				

Table 122: Number and Percentage of Subjects Experiencing Non-Serious, Related Unsolicited Adverse Events Within 21 Days Post Dose by MedDRA® System Organ Class and Preferred Term, Dose and Treatment Group – Safety Population *(continued)*

		Day 1-8 Post Dose 1		Day 9-22 Post Dose 1		Day 1-22 Post Dose 1		Day 1-8 Post Dose 2		Day 9-22 Post Dose 2		Day 1-22 Post Dose 2		Day 1-8 Post Dose 3		Day 1-8 Post Dose 3		Day 1-8 Post Dose 3		Day 1-22 Post Any Dose		
	[PT 2]																					
[SOC 2]	Any PT																					
	[PT 1]																					
	[PT 2]																					
Note: N = Number of subjects in the Safety Analysis Population. This table presents number and percentage of subjects. For each time period, a subject is only counted once per PT.																						

Table 123: Number of Unsolicited Adverse Events by MedDRA® System Organ Class and Preferred Term, Day Post Dose, and Treatment Group – Safety Population

			Day 1-8 Post Dose 1	Day 9-22 Post Dose 1	Day 1-22 Post Dose 1	Day 1-8 Post Dose 2	Day 9-22 Post Dose 2	Day 1-22 Post Dose 2	Day 1-8 Post Dose 3	Day 9-22 Post Dose 3	Day 1-22 Post Dose 3	Day 1-22 Post Any Dose
Treatment Group	MedDRA® System Organ Class	MedDRA® Preferred Term	# of Events	# of Events	# of Events	# of Events	# of Events	# of Events	# of Events	# of Events	# of Events	# of Events
Group 1: Simultaneous Administration (N=X)	Any SOC	Any PT	x	x	x	x	x	x	NA	NA	NA	x
	[SOC 1]	Any PT										
		[PT 1]										
		[PT 2]										
	[SOC 2]	Any PT										
		[PT 1]										
		[PT 2]										
Group 2: Sequential Administration (N=X)	Any SOC	Any PT	x	x	x	x	x	x	x	x	x	x
	[SOC 1]	Any PT										
		[PT 1]										
		[PT 2]										
	[SOC 2]	Any PT										
		[PT 1]										
		[PT 2]										
Group 3: IIV4 Only (N=X)	Any SOC	Any PT	x	x	x	NA	NA	NA	NA	NA	NA	x

Table 123: Number of Unsolicited Adverse Events by MedDRA® System Organ Class and Preferred Term, Day Post Dose, and Treatment Group – Safety Population *(continued)*

			Day 1-8 Post Dose 1	Day 9-22 Post Dose 1	Day 1-22 Post Dose 1	Day 1-8 Post Dose 2	Day 9-22 Post Dose 2	Day 1-22 Post Dose 2	Day 1-8 Post Dose 3	Day 9-22 Post Dose 3	Day 1-22 Post Dose 3	Day 1-22 Post Any Dose
	[SOC 1]	Any PT										
		[PT 1]										
		[PT 2]										
	[SOC 2]	Any PT										
		[PT 1]										
		[PT 2]										

Note: N = Number of subjects in the Safety Analysis Population. This table presents number of events; a subject may be counted multiple times.

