3.2.2. Secondary

Safety:

- Occurrence of study vaccine-related unsolicited non-serious AEs following each study vaccination through approximately 21 days after each study vaccination.
- Occurrence of all unsolicited non-SAEs following each study vaccination through approximately 21 days after each study vaccination.
- Occurrence of MAAEs, including NOCMCs and PIMMCs, following the first study vaccination through approximately 12 months after the last study vaccination.

Immunogenicity:

- For HAI and Neut antibodies, percentage of subjects achieving seroconversion against the 2017 H7N9 vaccine strain at approximately 21 days after receipt of 1 dose of AS03-adjuvanted 2017 H7N9 IIV (Group 1– Day 22; Group 2 – Day 43; Group 3 – N/A).
- For HAI and Neut antibodies, percentage of subjects achieving serum HAI and Neut antibody titers $\geq 1:40$ against the influenza 2017 H7N9 vaccine strain at baseline and approximately 21 days after receipt of 1 dose of AS03-adjuvanted 2017 H7N9 IIV (Group 1–Day 1 (baseline) and Day 22; Group 2 –Day 22 (baseline) and Day 43; Group 3 – N/A).
- GMTs of serum HAI and Neut antibodies against the influenza 2017 H7N9 vaccine virus at baseline and at approximately 21 days after receipt of 1 dose of AS03-adjuvanted 2017 H7N9 IIV. (Group 1–Day 1 (baseline) and Day 22; Group 2 –Day 22 (baseline) and Day 43; Group 3 – N/A).

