9.3.2. Unsolicited Adverse Events

When calculating the incidence of unsolicited AEs (i.e., on a per subject basis), each subject will only be counted once at the highest severity and/or relationship, and any repetitions of AEs within a subject will be ignored; the denominator will be the total number of subjects in the safety population. All AEs reported will be included in the summaries and analyses.

The number and percentage of subjects reporting at least one unsolicited AE will be summarized by MedDRA system organ class and preferred term. A 95% CI will be presented for the percentage of subjects reporting any unsolicited AE (serious or non-serious) for each MedDRA system organ class and preferred term over all study vaccinations ([Table 118](#)).

The following summaries for unsolicited AEs will be presented by MedDRA system organ class, preferred term, and treatment group:

- Incidence of AEs by severity and relationship to study product ([Table 119](#));
- Incidence of non-serious, related AEs by severity ([Table 120](#));
- Incidence of AEs over time (Days 1-8, Days 9-22 post each study vaccination) ([Table 121](#));

- Incidence of non-serious, related AEs over time (Days 1-8, Days 9-22 post each study vaccination) ([Table 122](#)) – note this table presents results for secondary safety endpoint, “Occurrence of study vaccine-related unsolicited non-serious AEs from the time of each study vaccination through approximately 21 days after each study vaccination”;
- Total frequency of AEs over time (Days 1-8, Days 9-22 post each study vaccination) ([Table 123](#));
- Subject listing of non-serious AEs of moderate or greater severity ([Table 128](#));
- Bar chart displaying total frequency of AEs by severity and MedDRA system organ class and treatment group ([Figure 54](#));
- Bar chart displaying incidence of AEs by severity and MedDRA system organ class, and treatment group ([Figure 55](#));
- Bar chart displaying total frequency and incidence of AEs by relationship to study product, MedDRA system organ class, and treatment group ([Figure 56](#) and [Figure 57](#)).

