9.7. Vital Signs and Physical Evaluations

Vital signs oral temperature, systolic blood pressure, diastolic blood pressure, and pulse will be assessed prior to study vaccination on Day 1 and Day 22. The grading scale for vital sign evaluations is presented in [Table 15](#). Summaries of vital signs by maximum severity will be tabulated by visit, and treatment group ([Table 144](#), [Table 145](#), [Table 146](#), [Table 147](#), [Table 148](#)). A listing of vital signs will be presented ([Listing 15](#)).

Targeted physical examinations will be performed, if indicated, based a subject's medical history. A listing of physical exam findings will be presented ([Listing 16](#)).

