9.8. Concomitant Medications

Concomitant medications will be collected for the 30 days prior to the first study vaccination through 21 days after the second study vaccination. Concomitant medications will be coded to the Anatomical Therapeutic Classification using the WHO Drug Dictionary. The use of prior and concomitant medications taken during the study will be recorded on the CRFs. A by-subject listing of concomitant medication use will be presented ([Listing 17](#)). The use of concomitant medications during the study will be summarized by ATC1, ATC2 code, treatment group for the Safety population ([Table 149](#)).

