[Implementation Note: A generic sample figure is shown below. Planned Study Day is plotted along the x-axis, with visit labels as tick labels. Titer is plotted on the y-axis on the log-10 scale. GMT should be plotted at each visit with upper and lower error bars for the 95% CI for each treatment group with different marker shapes/colors for each treatment group. Each treatment group should have a separate color and marker shape]

Note: this figure will be generated for the preliminary report including data through Day 43, then re-generated for the final CSR to include all data through Day 202.

Figures with similar format:

Figure 23: Geometric Mean Titers of Hemagglutination Inhibition Antibody against 2017 A/H7N9 by Study Day and Treatment Group, Per Protocol Population*

Figure 24: Geometric Mean Titers of Neutralizing Antibody against 2017 A/H7N9 by Study Day and Treatment Group, Modified Intent to Treat Population*

Figure 25: Geometric Mean Titers of Neutralizing Antibody against 2017 A/H7N9 by Study Day and Treatment Group, Per Protocol Population*

Figure 26: Geometric Mean Titers of Hemagglutination Inhibition Antibody Against A/Michigan/45/2015 X-275(H1N1) by Study Day and Treatment Group, Modified Intent to Treat Population*

Figure 27: Geometric Mean Titers of Hemagglutination Inhibition Antibody against A/Michigan/45/2015 X-275(H1N1) by Study Day and Treatment Group, Per Protocol Population*

Figure 28: Geometric Mean Titers of Neutralizing Antibody against A/Michigan/45/2015 X-275(H1N1) by Study Day and Treatment Group, Modified Intent to Treat Population*

Figure 29: Geometric Mean Titers of Neutralizing Antibody against A/Michigan/45/2015 X-275(H1N1) by Study Day and Treatment Group, Per Protocol Population*

Figure 30: Geometric Mean Titers of Hemagglutination Inhibition Antibody Against A/Hong Kong/4801/2014 X263B (H3N2) by Study Day and Treatment Group, Modified Intent to Treat Population*

Figure 31: Geometric Mean Titers of Hemagglutination Inhibition Antibody against A/Hong Kong/4801/2014 X263B (H3N2) by Study Day and Treatment Group, Per Protocol Population*

- Figure 32: Geometric Mean Titers of Neutralizing Antibody against A/Hong Kong/4801/2014 X263B (H3N2) by Study Day and Treatment Group, Modified Intent to Treat Population***
- Figure 33: Geometric Mean Titers of Neutralizing Antibody against A/Hong Kong/4801/2014 X263B (H3N2) by Study Day and Treatment Group, Per Protocol Population***

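### The GMT figure note uses Group 1's cut-off days, so the four H7N9 plots omit Group 2's Day 64 (preliminary report) and Day 223 (CSR); SAP 9.8 also ends the medication window too early

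*SAP*

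**What the plan says.** **GMT figures.** SAP Appendix 2 (14.2.2, note to Figure 22) plots GMT against planned study day. It has the figure made for the preliminary report "including data through Day 43, then re-generated for the final CSR to include all data through Day 202". Figures 23-41 are listed as having a similar format. Figures 22-25 show H7N9 (two assays, two populations). Figures 26-41 show the four IIV4 strains.

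**Concomitant medications.** SAP 9.8 sets the window from 30 days before the first vaccination "through 21 days after the second study vaccination". SAP 4.4.7 runs it to 21 days after the final dose, and protocol 6.6 to about 21 days after the last vaccination.

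**Unsolicited AEs by period.** SAP 9.3.2 specifies "Incidence of AEs over time (Days 1-8, Days 9-22 post each study vaccination" for Table 121 and the matching related, non-serious summary for Table 122. It names Table 122 as the display of a secondary safety endpoint. In both shells the three Dose 3 columns carry the same head, "Day 1-8 Post Dose 3".

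**Vital signs.** SAP 9.7 says they "will be assessed prior to study vaccination on Day 1 and Day 22". Protocol 7.1 adds Day 43 where the group is vaccinated then.

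**The concern.** Groups 1 and 2 reach the same H7N9 milestones on different study days, because Group 2 starts H7N9 three weeks later. A plot on study day that stops at Group 1's milestones shows Group 1 after its full course and Group 2 part-way through. Figures 22-25 are starred for the preliminary report. SAP 6.2.1 treats that report as the final analysis of its data and allows it to go to the lead investigator for publication. A reader of the preliminary figure could take a gap at Day 43 for an effect of schedule, when it is at least partly a difference in the number of H7N9 doses received.

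The medication sentence raises a smaller issue. A programmer working from SAP 9.8 alone would leave out of Table 149 and Listing 17 the weeks after the last dose.

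**Working it through.** **1. Reproduce the sampling days.** Inputs are the dose days in SAP Table 1 and the sampling days in SAP 4.1. H7N9 is given on Days 1 and 22 in Group 1, and on Days 22 and 43 in Group 2.

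- Group 1, 21 and 180 days after the second H7N9 dose: 22 + 21 = 43; 22 + 180 = 202.
- Group 2, 21 and 180 days after the second H7N9 dose: 43 + 21 = 64; 43 + 180 = 223.

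These match SAP 4.1.

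**2. Apply the Figure 22 cut-offs to the scheduled H7N9 points.**

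| | Scheduled | Kept through Day 43 | Kept through Day 202 |
|---|---|---|---|
| Group 1 | 1, 22, 43, 202 | 1, 22, 43 | 1, 22, 43, 202 |
| Group 2 | 22, 43, 64, 223 | 22, 43 | 22, 43, 64 |

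Day 64 is missing from the preliminary version only. Day 223 is missing from the CSR version only. At Day 43 Group 1 is 21 days past its second H7N9 dose. Group 2 is 21 days past its first and gives blood before its second.

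**3. Compare with the rest of the SAP.** SAP 6.2.1 puts HAI and Neut results through Day 64 in the preliminary report. The note to Figure 2 uses Day 64 for the reverse cumulative curves. Tables 28-31 have a row for 21 days after Dose 3 and one for 180 days after the second H7N9 dose (Day 223 in Group 2). SAP 12 records no departure from the protocol, so the figure cut-off is not a documented choice.

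**4. Count the figures affected.** Figures 22-41 are 20 figures, of which 4 plot H7N9 and 16 plot IIV4. SAP 4.1 schedules IIV4 assays at Day 1 and about 21 and 180 days after IIV4 (Days 22 and 181). All of these fall inside the cut-offs. The Table 32 shell has later IIV4 rows, but SAP 4.1 does not schedule IIV4 assays for them.

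**5. Medication window.** SAP Table 1 counts Group 1's two Day 1 injections as its first and second study vaccinations.

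- Group 2: second vaccination Day 22, so 22 + 21 = Day 43. Last vaccination Day 43, so 43 + 21 = Day 64. Shortfall 21 days.
- Group 1, Table 1 numbering: 1 + 21 = Day 22, against 22 + 21 = Day 43. Shortfall 21 days. If the sentence meant Dose 2, the result is Day 43 and nothing is lost.
- Group 3 has one vaccination, so SAP 9.8 gives it no end date.

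**6. Tables 121-122 against Table 123.** Each has ten period columns: three for each of three doses, and one for any dose. Eight heads agree. The second and third Dose 3 heads repeat "Day 1-8 Post Dose 3" where Table 123 has "Day 9-22 Post Dose 3" and the Day 1-22 head. The shells mark all three as applicable to Group 2.

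**7. Vital signs.** The SAP 9.7 sentence names 2 of Group 2's 3 days. Tables 144 and 146 give Group 2 a Day 43 row and mark it not applicable for Groups 1 and 3.

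**The case against.** The strongest reply is that nothing inferential rests on Figure 22. Tables 28-31 are starred for the preliminary report and hold Group 2's values at 21 days after Dose 3. The 21-day regression tables compare the groups at the same interval after the second H7N9 dose. SAP 6.2.1 already includes Day 64 data, so a programmer may well extend the plot. This stands, and it limits the point to display and consistency. It does not make the note right: the note gives explicit days, and they conflict with SAP 6.2.1.

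A reader might also infer that Group 2's third-dose period is dropped from the unsolicited-AE tables, with Days 9-22 lost, and so that the endpoint "Occurrence of all unsolicited non-SAEs following each study vaccination through approximately 21 days after each study vaccination" would be incomplete. The documents do not support that. The columns are present, SAP 9.3.2 and Table 123 settle their labels, and a column for any dose is also there. The same inference fails for vital signs, because the shells display Day 43.

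Nor is there good ground for saying that SAP 9.8 damages the per-protocol population. The SAP schedules for Group 2 collect medications at Days 43, 50 and 64. SAP 7.2 makes per-protocol exclusions through review of deviations. The immunosuppressant rule spans 30 days around each vaccination, which a 21-day window would not fully cover in any case.

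**Conclusion.** The Figure 22 note is wrong as written for Figures 22-25. Group 2 loses one of its three H7N9 points due by Day 64 in the preliminary version, and one of four in the CSR version. Group 1 loses none. No primary or secondary estimate is lost. SAP 9.8 is also wrong as written: it is 21 days short in Group 2, 21 days short in Group 1 under Table 1 numbering, and undefined for Group 3. The repeated heads in Tables 121-122 and the missing day in SAP 9.7 are editorial.

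Two wider readings should not be drawn. The effect does not reach all 20 GMT figures, since the scheduled IIV4 points lie within the cut-offs. A single cause, such as text carried over from a two-dose study, is not shown: Tables 121-122 already have a three-dose layout, and Days 43 and 202 are this trial's own Group 1 days.

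The conclusion assumes that the note is programmed literally and that assays follow SAP 4.1. It is a minor point, worth correcting because the figures are due for early release.

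**What to change.** 1. Note to Figure 22: change the cut-offs to Day 64 for the preliminary report and Day 223 for the CSR, in line with SAP 6.2.1, the Figure 2 note and SAP 4.1.
2. SAP 9.8: end the window 21 days after the last study vaccination, as in SAP 4.4.7 and protocol 6.6. This also gives Group 3 an end date.
3. Tables 121-122 (editorial): relabel the second and third Dose 3 heads as Day 9-22 and Day 1-22, as in Table 123.
4. SAP 9.7 (editorial): add Day 43 for Group 2, to match protocol 7.1 and Tables 144-148.

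The cost is a few words of SAP text and shell labels. No data collection, sample size or analysis model changes.
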